8.3.1 Visit 6 (Day 22)

The following assessments will be performed.

Information and procedures listed below will be collected/completed by the investigator and/or study staff, as appropriate, via a telephone or telemedicine call with the subject/legal representative.

- Withdrawal criteria
- Menstrual function for all female subjects

For lab collections and procedures listed below, mobile study personnel will be sent to the subject's/legal representative's home. Samples will be prepared and sent to a central laboratory for processing and analysis, and results will be provided to the study site.

- Vital signs
- Body weight, height, and BMI
- Safety laboratory tests
- Urine pregnancy test for all female subjects
- PK sampling—record sampling time, time of application of study medication, and application site of study medication in eCRF

Assessments listed below will be completed either by the subject or investigator/trained study staff, as required. Assessments that require interviews will be completed via a telephone or telemedicine call.

- C-SSRS (Since Last Visit version)
- IRLS
- CGI
- RLS-6
- mMIDI
- Subject Quality of Life Questionnaire

Additional assessments and procedures are listed below.

- Recording of medication and procedures. See [Section 8.2.1](#).
- AE assessment. See [Section 8.2.1](#).
- Contact IRT. The IRT will be contacted to obtain study medication kit numbers for the Maintenance Period.

- Dispense study medication. Study medication for the Maintenance Period will be distributed. See [Section 7.5](#) for a description of the direct-to-subject shipment process for the remote study model.
- Return any unused study medication. Subjects/legal representatives will return the unused study medication patches remaining as part of the medication kits, along with the kit itself. Upon receipt of this return, designated study staff will review drug accountability with the participant via a telephone or telemedicine call to obtain explanations regarding any discrepancies in compliance with the dosing regimen.

8.3.2 Visit 7 (Day 50) and Visit 8 (Day 78)

The following assessments will be performed at Visit 7 and Visit 8 via telemedicine call.

Information and procedures listed below will be collected/completed by the investigator and/or study staff, as appropriate, via a telemedicine call with the subject/legal representative.

- Withdrawal criteria

Assessments listed below will be completed either by the subject or investigator/trained study staff, as required. Assessments that require interviews will be completed via a telephone or telemedicine call.

- C-SSRS (Since Last Visit version)
- IRLS
- CGI
- RLS-6

Additional assessments and procedures are listed below.

- Recording of medication and procedures. See [Section 8.2.1](#).
- AE assessment. See [Section 8.2.1](#).
- Contact IRT. The IRT will be contacted to obtain study medication kit assignments.
- Dispense study medication. Study medication for the Maintenance Period will be distributed. See [Section 7.5](#) for the description of the direct-to-subject shipment process for the remote study model.
- Return any unused study medication. See [Section 8.3.1](#).

8.3.3 Visit 9 (Day 106)/End of Maintenance

The following assessments will be performed.

Information and procedures listed below will be collected/completed by the investigator and/or study staff, as appropriate, via a telephone or telemedicine call with the subject/legal representative.

- Withdrawal criteria
- Menstrual function for all female subjects

Assessments listed below will be completed by mobile study personnel at the subject's/legal representative's home and records of the procedures will be obtained, with information noted as part of the subject's study record.

- Brief physical examination, including body weight, height, BMI, and vital signs
- Neurological examination
- 12-lead ECG

For lab collections and procedures listed below, mobile study personnel will be sent to the subject's/legal representative's home. Samples will be prepared and sent to a central laboratory for processing and analysis, and results will be provided to the study site.

- Safety laboratory tests
- Urine pregnancy test for all female subjects
- Hormone status
- PK sampling—record sampling time, time of application of study medication, and application site of study medication in eCRF

Assessments listed below will be completed either by the subject or investigator/trained study staff, as required. Assessments that require interviews will be completed via a telephone or telemedicine call.

- C-SSRS (Since Last Visit version)
- IRLS
- CGI
- RLS-6
- mMIDI
- Subject Quality of Life Questionnaire

Additional assessments and procedures are listed below.

- Recording of medication and procedures: See [Section 8.2.1](#).
- AE assessment: See [Section 8.2.1](#).
- Contact IRT: The IRT will be contacted to obtain study medication kit numbers for the Taper Period.
- Dispense study medication for the Taper Period. See [Section 7.5](#) for the description of the direct-to-subject shipment process for the remote study model.
- Return any unused study medication

8.4 Taper Period (Day 106 to Day 110)

The Taper Period, which will last up to a maximum of 4 days, will start on the day after Visit 9 and will consist of a telemedicine call. The de-escalation study medication to be taken during the Taper Period will be dispensed at Visit 9.

8.5 Safety Follow-Up Visit (if applicable)

The visit window for Safety Follow-Up Period is 30 days \pm 5 days relative to the end of the Taper Period. Following dose de-escalation, subjects may be eligible to participate in the open-label, long-term follow-up study (RL0007) at any time prior to the Safety Follow-Up Visit (see [Section 5](#)). The Safety Follow-Up Visit is for subjects not entering RL0007.

Information listed below will be collected by the investigator and/or study staff, as appropriate, via a telephone or telemedicine call with the subject/legal representative.

- Menstrual function for all female subjects

The assessments listed below will be completed by mobile study personnel at the subject's/legal representative's home and records of the procedures will be obtained, with information noted as part of the subject's study record.

- Brief physical examination, including body weight, height, BMI, and vital signs
- Neurological examination
- 12-lead ECG

For lab collections and procedures listed below, mobile study personnel will be sent to the subject's/legal representative's home. Samples will be prepared and sent to a central laboratory for processing and analysis, and results will be provided to the study site.

- Safety laboratory tests
- Urine pregnancy test for all female subjects
- Hormone status

Assessments listed below will be completed either by the subject or investigator/trained study staff, as required. Assessments that require interviews will be completed via a telephone or telemedicine call.

- C-SSRS (Since Last Visit version)

Additional assessments and procedures are listed below.

- Recording of medication and procedures. See [Section 8.2.1](#).
- AE assessment. See [Section 8.2.1](#).
- Contact IRT. The IRT is contacted to process the subject's completion of the study.
- Return unused study medication. See [Section 8.3.1](#).

8.6 Withdrawal Visit

Procedures for a withdrawal visit are the same as for Visit 9.

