6.3.1 Potential drug-induced liver injury IMP discontinuation criteria

Subjects with potential drug-induced liver injury (PDILI) must be assessed to determine if IMP must be discontinued. In addition, all concomitant medications and herbal supplements that are not medically necessary should also be discontinued.

The PDILI criteria below require immediate and permanent discontinuation of IMP:

- Subjects with either of the following:
 - ALT or AST $\geq 5xULN$
 - ALT or AST $\geq 3xULN$ and coexisting total bilirubin $\geq 2xULN$

The PDILI criterion below requires immediate discontinuation of IMP:

- Subjects with ALT or AST $\geq 3xULN$ who exhibit temporally associated symptoms of hepatitis or hypersensitivity. Hepatitis symptoms include fatigue, nausea, vomiting, right upper quadrant pain or tenderness. Hypersensitivity symptoms include fever (without clear alternative cause), rash, or eosinophilia (ie, $>5\%$).

If a nondrug-related cause for the symptoms can be confirmed, these subjects may resume IMP administration after discussion with the responsible UCB physician, but only when the requirements for rechallenge with IMP as provided in [Section 11.6.1.2](#) are followed.

The PDILI criterion below allows for subjects to continue on IMP at the discretion of the investigator.

- Subjects with ALT or AST $\geq 3xULN$ (and $\geq 2x$ baseline) and $<5xULN$, total bilirubin $<2xULN$, and no eosinophilia (ie, $\leq 5\%$), with no fever, rash, or symptoms of hepatitis (eg, fatigue, nausea, vomiting, right upper quadrant pain or tenderness).

Evaluation of PDILI must be initiated as described in [Section 11.6.1](#). If subjects are unable to comply with the applicable monitoring schedule, IMP must be discontinued immediately.

Investigators should attempt to obtain information on subjects in the case of IMP discontinuation to complete the final evaluation. Subjects with PDILI should not be withdrawn from the study until investigation and monitoring are complete. All results of these evaluations and observations, as well as the reason(s) for IMP discontinuation and subject withdrawal (if applicable), must be recorded in the source documents. The eCRF must document the primary reason for IMP discontinuation.

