13.3 Planned efficacy analyses

13.3.1 Analysis of the co-primary efficacy variables

Mean changes from Baseline to the end of the Maintenance Period in IRLS sum score and CGI (Item 1) in the 2 rotigotine arms (2mg/24h and 3mg/24h) will be compared with placebo to demonstrate superior efficacy of rotigotine.

The primary analysis of each co-primary variable will be based on a mixed model repeated measures (MMRM) analysis of covariance (ANCOVA) that includes terms for treatment group, visit, the respective Baseline score, and the interaction between treatment group and visit. The model will define patient as a random effect and utilize an unstructured covariance pattern. From this MMRM ANCOVA, treatment least-square (LS) means (with 95% confidence intervals [CI]) will be calculated and 1-sided 2 sample t-test will be performed (significance level 0.025) to test

the superiority of the rotigotine dose levels versus placebo, starting with 3mg/24h. The corresponding p-values will also be calculated.

The null hypotheses at each dose level are (H0): rotigotine is not superior compared to placebo. The alternative hypotheses are (H1): rotigotine is superior to placebo. Both co-primary endpoints must demonstrate significant results (at significance level 0.025) to demonstrate superiority of this dose level of rotigotine over placebo.

If the 3mg/24h dose is successful, the 2mg/24h dose level will be tested in the same way. Since both hypotheses have to be rejected in order to continue, multiplicity adjustment is not needed for the 2 hypotheses at each dose level. The multiplicity based on the two dose levels will be covered by applying the hierarchical approach (closed test procedure).

For subjects who prematurely withdraw for any reason before end of Maintenance, data collected during the Withdrawal Visit will be used to impute measurements at the next consecutive visit.

IRLS or CGI-1 measurements must be performed no longer than 1 day after the last patch removal to be utilized for analysis (valid measurements).

The above analyses will be performed on the FAS and the PPS. The primary analysis will be considered the analysis on the FAS.

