13.8 Determination of sample size

The sample size estimate is based on the efficacy results observed in the adult RLS Phase 3 confirmatory study SP792, which was conducted in the USA. In this study, a range of rotigotine doses were compared to placebo.

The sample size calculation assumes that adolescent and adult patients will show a similar effect of rotigotine with respect to IRLS score and CGI (item 1) changes from Baseline in comparison to placebo, with a similar proportion of patients not included in the primary analysis.

In the adult study, the observed difference between the 3mg/24h rotigotine group and placebo in the change from Baseline to end of the 3-month Maintenance Period in IRLS sum score was 5.9. Already a difference between rotigotine and placebo of 4.0 points can be considered as clinically relevant. The common Standard Deviation (SD) estimate in the adult study was 7.9. For the CGI (Item 1), the difference between 3mg/24h rotigotine group and placebo was 0.6 with a SD of 1.2.

With these assumptions, a sample size of 45 evaluable patients in each group will provide a power of 93% for the IRLS endpoint, and a power of 87% for the CGI (Item 1) endpoint in the 3mg/24h dose. Assuming independence of the 2 endpoints will result in a power of 80% for the analysis of the co-primary variables. Since it is known that the 2 endpoints will have a relatively high correlation (approximately 0.7), the calculated 80% is a conservative estimator for the power.

Assuming similar effects for the 2mg/24h dose group, the conditional power for the 2mg/24h dose group is also 80% with an overall power for the study >60%. To obtain 135 evaluable subjects (ie, FAS), 138 patients have to be randomized (assuming approximately 2% of the randomized subjects cannot be utilized).

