3.2.1.2 Date of last patch removal

The date of last patch application is documented on the Study Termination page of the eCRF. If the date of last patch application on this page is missing the last available kit start date on the Drug Accountability log form will be used as the date of last patch application. Thus, the date of the last patch removal is defined as the date of the last patch application + 1.

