3.2.2 Study periods

The following time periods are defined for this study.

- Screening Period:

The Screening Period starts with Visit 1 and ends the day before the date of the first patch application. This period includes Visit 2/Day 0 at which the subjects are randomized, and study medication is assigned and shipped.

- Titration Period:

The Titration Period starts at the day of the first patch application (Day 1) and ends on the day prior to Visit 6. In case of a premature withdrawal before Visit 6, the Titration Period ends at the day of the Withdrawal Visit. If the Withdrawal Visit is missing or the date of the last patch removal (or last known patch removal) is before the Withdrawal Visit, the Titration Period ends at the day of last patch removal.

- Maintenance Period:

The Maintenance Period starts at Visit 6 and ends at Visit 9. If the subject withdraws prior to Visit 9, the Maintenance Period ends at the day of the Withdrawal Visit date or the last patch removal date (or last known patch removal date), whichever is earlier.

- Taper Period:

The Taper Period starts at the date of last maintenance patch removal and ends at the day of last patch removal. If the day of last patch removal is on the date of last maintenance patch removal, i.e., no de-escalation was performed for any reason, then no Taper Period is defined for this subject.

- Treatment Period:

The Treatment Period comprises the Titration Period, the Maintenance Period, and the Taper Period, i.e., it starts with the day of first patch application and ends on the maximum end date of the Titration, Maintenance and Taper periods.

- Safety Follow-Up Period:

The Safety Follow-Up Period starts the day after the end of the Treatment Period and ends at the date of the Safety Follow-Up Visit. However, AEs starting within 30 days following the date of last patch removal will be considered for analysis, even if the start date is after the

date of last study assessment. If the subject rolls over into the RL0007 study, then the Safety Follow-up Period dates will be missing.

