3.5.4 Full Analysis Set (FAS)

The FAS will consist of all subjects from the SS who have a valid IRLS score with a valid post-Baseline IRLS score or a valid CGI Item 1 score at Baseline paired with a valid post-Baseline CGI Item 1 score. This population is the primary population for efficacy analysis.

A valid IRLS or CGI Item 1 score at Baseline is defined as a completely answered questionnaire on or before the date of first study medication. A valid post-Baseline IRLS or CGI Item 1 score is defined as a completely answered questionnaire during the Treatment Period, i.e., measured after Baseline and on or before one day after the last patch removal.

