4.2.1 Missing efficacy data

For subjects who prematurely withdraw for any reason before EoM, values for planned efficacy assessments scheduled at subsequent visits will not be imputed. Efficacy assessments must be performed no later than 1 day after the last patch removal to be utilized for analysis (valid measurements).

For IRLS analysis, if any item is missing, the IRLS sum score will not be calculated. Missing IRLS baseline items and therefore the total score will be regarded as an important protocol deviation.

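### The Withdrawal Visit is not timed to the last patch, so subjects who stop patches first can miss the 1-day limit on IRLS and CGI Item 1 and, before Visit 6, can lose their FAS place

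*Protocol*

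**What the plan says.** - **Content of the visit.** Protocol 8.6 reads "Procedures for a withdrawal visit are the same as for Visit 9". Table 5-1 puts the Withdrawal Visit in the Visit 9 column. Neither place, nor the withdrawal criteria in 6.3, sets a time from the last patch.
- **Validity limit.** Protocol 13.3.1 and SAP 4.2.1 accept efficacy scores only up to 1 day after the last patch comes off. SAP 3.5.4 counts a post-Baseline score only if it is "measured after Baseline and on or before one day after the last patch removal". SAP 3.2.1.2 fixes the removal date: "the date of the last patch removal is defined as the date of the last patch application + 1".
- **Schedule of the scales.** IRLS and CGI Item 1 are taken at Screening, Baseline and Visits 6 to 9 (Protocol 9.1, 9.2). Visits 4 and 5 collect neither scale (8.2.3), and the Unscheduled Visit list in 8.7 names neither.
- **FAS.** Protocol 13.1 requires valid Baseline and post-Baseline scores on both scales. SAP 3.5.4 accepts either scale.
- **Liver injury.** Protocol 6.3.1 has tiers in which study drug stops at once, and adds: "Subjects with PDILI should not be withdrawn from the study until investigation and monitoring are complete". Table 11-3 sets liver monitoring at least twice a week until the values settle.
- **Dating rule.** SAP 3.2.2 ends the Titration Period at the last patch removal "If the Withdrawal Visit is missing or the date of the last patch removal (or last known patch removal) is before the Withdrawal Visit".

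**The concern.** The plan has a strict rule on which scores count and no instruction that makes sites meet it. For a subject who leaves during titration, the Withdrawal Visit supplies the only post-Baseline IRLS and CGI Item 1, so its timing decides FAS membership. For a subject who leaves during Maintenance, it supplies the last on-treatment score. The protocol would use that score at the next visit (13.3.1), and SAP 4.2 assigns it to the next scheduled visit in the by-visit summaries.

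Being scored late depends on having stopped patches before the visit, which is a post-randomization event. If such stops are more frequent on rotigotine than on placebo, which is plausible but not quantified in the documents, the primary efficacy population is partly selected by tolerability.

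**Working it through.** **1. Last usable day.** Let A be the day of the last patch application.
- Removal (SAP 3.2.1.2): R = A + 1.
- Last valid score (SAP 3.5.4): R + 1 = A + 2.
- Example: last application on Day 10, removal on Day 11. A score on Day 12 counts and a score on Day 13 does not.

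**2. Routes into the FAS for a stop on Days 1 to 21.**

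| Contact | IRLS / CGI Item 1 listed? | Timed to the last patch? |
|---|---|---|
| Visits 3, 4, 5 | No | n/a |
| Unscheduled Visit (8.7) | No | n/a |
| Visit 6, Day 22 | Yes | Past A + 2 for any last application before Day 20 |
| Withdrawal Visit (8.6) | Yes | No |

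The Withdrawal Visit is in practice the only route, and nothing obliges the site to take the scores by A + 2.

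**3. Permanent liver-injury stop before Visit 9.** Study drug stops at once, so the limit falls at A + 2. Study withdrawal waits until investigation and monitoring are complete, with laboratory checks at least twice weekly in the meantime. A Withdrawal Visit held at withdrawal then falls after A + 2 even though the site has followed the protocol.

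**4. The plan's allowance.** Protocol 13.8 aims for 135 evaluable subjects, "assuming approximately 2% of the randomized subjects cannot be utilized".
- 135 / (1 − 0.02) = 137.8, rounded up to 138. This reproduces the stated figure.
- Allowance: 138 − 135 = 3 subjects, or 3/138 = 2.2%, about 1 per arm, for all causes.

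**5. Illustrative loss (both rates are assumptions).** Suppose 5% to 10% of each active arm (138/3 = 46) stop patches in titration and half of them are scored late.
- Per active arm: 46 × 0.05 × 0.5 = 1.2; 46 × 0.10 × 0.5 = 2.3.
- Two active arms: 2.3 to 4.6 subjects, or 1.7% to 3.3% of 138.

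**6. What total FAS loss would do to the planned power.** Two-sample t-test, one-sided 0.025, noncentrality Δ / (SD × √(2/n)).
- IRLS, 5.9 / 7.9, n = 45: noncentrality 3.54, power 93.9% (stated 93%).
- CGI Item 1, 0.8 / 1.2 (SAP 2.5), n = 45: noncentrality 3.16, power 87.9% (stated 87%). Protocol 13.8 prints 0.6 instead, which gives 65.0% and does not reproduce 87%, so 0.8 is used here. That discrepancy is a separate matter.
- Stated joint power: 0.93 × 0.87 = 80.9% (stated 80%).

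With the loss spread evenly over arms and the two endpoints taken as independent, as the plan does:

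| FAS loss, all causes | FAS | n per arm | IRLS | CGI Item 1 | Joint | Randomized N to keep 135 |
|---|---|---|---|---|---|---|
| 2% | 135 | 45.1 | 93.9% | 87.9% | 82.6% | 138 |
| 5% | 131 | 43.7 | 93.2% | 86.9% | 81.0% | 143 |
| 10% | 124 | 41.4 | 91.9% | 85.0% | 78.1% | 150 |
| 15% | 117 | 39.1 | 90.3% | 82.9% | 74.9% | 159 |
| 20% | 110 | 36.8 | 88.5% | 80.5% | 71.3% | 169 |

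Joint power drops below 80% somewhere between 5% and 10% total loss. The loss in step 5 alone would not take it there.

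**The case against.** The strongest reply is that the timing link already exists. Protocol 13.3.1 states the 1-day limit, and Visit 9, which 8.6 copies, lists the scales apart from the mobile-personnel procedures, with interviews by phone or telemedicine. A site can meet the limit. Visit 9 also dispenses taper supply, so a subject who tapers after the visit is scored while still on patches. Subjects are told to speak to the investigator before stopping (7.2.4). Dopaminergic adverse events in titration lead to back-titration, and withdrawal is prescribed only for first-week intolerance (5.1). The earlier adolescent study reported no adverse event leading to discontinuation (5.4), although it was small, open-label and under 5 weeks long.

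All of this limits how often a score is lost, and the rate may be low. It does not close the gap, because the limit sits in the statistics section while the visit instructions are silent.

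A reader might infer more than the documents support:
- **That every liver-injury stop loses its score.** One tier lets study drug resume and another lets it continue. Scheduled on-treatment safety laboratory tests are at Visits 6 and 9 (8.3.1, 8.3.3), where the scales are also taken. A stop found from Visit 6 tests keeps its FAS place, and one found from Visit 9 tests already has its end-of-Maintenance score. Losing the FAS place through liver injury in titration would need an unscheduled test. Section 6.3.1 also asks for information to complete the final evaluation when study drug stops, but without naming the scales or a time.
- **That a late home visit means a late score.** The scales do not depend on the home visit.
- **That the SAP expects removal before the Withdrawal Visit.** SAP 3.2.2 is a conditional dating rule, and it also covers removal one day before the visit, which is still valid.
- **That a confirmatory comparison is now at risk.** The current SAP follows early termination. It replaces the mixed model with summaries, drops the PPS and interim analyses, and lets either scale qualify a subject for the FAS.

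**Conclusion.** The point holds in a limited form. Subjects who stop patches before an untimed Withdrawal Visit can lose their withdrawal score, and those who stop before Visit 6 can leave the FAS. Permanent liver-injury stops before Visit 9 lose a later withdrawal score when 6.3.1 is followed as written.

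The size is unknown. The range of 2.3 to 4.6 subjects rests on two assumed rates, set against 3 allowed for all causes. It shows that a modest rate could use up the allowance and is not a forecast. That the losses would fall more on the active arms is plausible but also assumed. Under the present SAP the consequence is confined to who is in the FAS and what enters the descriptive by-visit tables. It is worth correcting because the remedy is cheap.

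**What to change.** In Protocol 8.6, with a footnote to Table 5-1, state that whenever study drug is stopped early for any reason:
- IRLS, CGI Item 1 and RLS-6 are completed by phone or telemedicine no later than 1 day after last patch removal, separately from the home visit.
- This also applies when study withdrawal is deferred under 6.3.1.
- These scores are recorded as the Withdrawal Visit efficacy assessment.

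Stopping, taper and monitoring rules stay as they are. The scales are already completed by the subject or by remote interview, so no new procedure is needed. The cost is a wording change and possibly one extra short call. It cannot recover scores already taken late in the terminated study.
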